The goal of this study is to develop and test the efficacy of a scientifically-based, culturally competent seven-session parent directed, obesity prevention program focused on parental feeding strategies that support young children's self-regulation of intake.

STUDY DESIGN

A randomized controlled trial will be implemented across 2 sites (Houston, an urban city in Texas; and Pasco, an agricultural community in Washington) to examine the efficacy of the SEEDS childhood obesity prevention program. The prevention arm will receive parent and child program curriculums separately over 7 weeks for a total of 7 lessons. One lesson will be held each week with parent and child lessons held simultaneously. Each lesson will last about an hour. A combined family lesson (parent and child together) will be held before the parent and child lessons. All lessons will be held after the school day in Spanish at Head Start centers in Houston, TX and similar early education centers in Pasco, WA. The control arm will receive no curriculum. Approximately 8 to 10 families will participate in each of the prevention and control conditions at each wave. Parents will be asked if they could read and write in English or Spanish during eligibility screening so that assistance can be made available at the data collection sessions for those who need help completing the questionnaires. Participants in the prevention and control arms will complete the same assessments prior to the prevention program (pretest), after the program (posttest), and at 6- and 12-month follow-ups. Participants will be compensated \$40 at pretest, \$50 at posttest, \$60 at 6 months, and \$85 at 12 months.

FACILITATORS

Bilingual staff members will lead the face-to-face groups (i.e., parent, child, and family lessons). Parent facilitators will be required to have a graduate degree in psychology or education to optimize behavior change that is integrated into the program content. Child facilitators will be required to have training or experience in early childhood education. Family lessons will be co-facilitated by the parent and child facilitators. Facilitator training will include a 2-day intensive training session guided by study investigators which will include coverage of the program

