All analyses will be intention-to-treat analyses—that is, data from parents and children will be analyzed based upon the condition to which they will be initially assigned, regardless of the number of classes they attended. This approach, although it reduces power, maintains the internal validity of the RCT design.⁵⁷ Because participants will be nested within classes, the intraclass correlations (ICC's) will be first examined for each dependent variable to determine if a statistical approach controlling for such nesting will be necessary. All outcome variables (except for child weight status) will be examined using multilevel analyses with the SPSS (version 25) Mixed Models Program. The SPSS Mixed Model program does not provide measures of effect sizes; however, 95% confidence intervals will be included for precision. Child sex, child age in months, and child BMIz at pre-test will be control variables in all of the multilevel analyses. Significant condition by time interactions will be followed up with simple main effects analyses and multi-level analyses comparing pairs of time points. The main analyses will be conducted on participants who have data at all 4 time points. Paired comparisons will use all available data. Most of the missing data will be addressed by calculating the subscale scores using the mean of the non-missing items in that particular subscale. If greater than 25% of a subscale's items are blank, then the score will be considered missing. The multilevel models also will be rerun examining (1 at a time) possible program moderators: child age, child sex, child BMI status, and location (Houston versus Pasco). Moderation will be tested by examining the significance of the moderator by condition by time interactions.

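### Sex, age and pretest BMIz, read as main-effect control variables, do not adjust the condition-by-time estimates in the four-visit completer analysis

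*Combined protocol and SAP*

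**What the plan says.** All of this is in the Data Analyses section unless another section is named.

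- Model: "All outcome variables (except for child weight status) will be examined using multilevel analyses with the SPSS (version 25) Mixed Models Program". No covariance structure or random effects are named, and whether to model class nesting depends on the observed intraclass correlations.
- Covariates: "Child sex, child age in months, and child BMIz at pre-test will be control variables in all of the multilevel analyses". Covariate-by-time terms are neither specified nor excluded.
- Visits (Study Design): "prior to the prevention program (pretest), after the program (posttest), and at 6- and 12-month follow-ups".
- Analysis set: "The main analyses will be conducted on participants who have data at all 4 time points".
- Deciding test and follow-up: "Significant condition by time interactions will be followed up with simple main effects analyses and multi-level analyses comparing pairs of time points". For the follow-up, "Paired comparisons will use all available data".
- Moderators (child age, sex, BMI status and location, one at a time): "Moderation will be tested by examining the significance of the moderator by condition by time interactions".

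The dosage paragraph likewise names an interaction of lessons attended with time where one is wanted. The BMI-category regression tests the main effect of condition with the same three covariates.

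**The concern.** The plan judges the program by whether the arms change differently over time. A variable that is fixed for each child and enters only as a main effect adds the same amount to all four visits, so it drops out of every change. A reader told that sex, age and BMIz were controlled would assume that the efficacy result was adjusted for them. On the main-effects reading, the condition-by-time estimate is not.

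Three features of the plan give this some weight:

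- Allocation is by simple randomization (Participant Eligibility and Recruitment), so no stratification limits chance imbalance.
- The main analysis is restricted to completers, whose balance randomization no longer guarantees.
- The paragraph on Type I error itself cites the limited power of condition-by-time interactions. Covariate-by-time terms could recover some precision in exactly that test.

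The Background also reports poorer energy compensation in older than in younger children. With ages 3 to 5 enrolled and 12 months of follow-up, it is plausible, though not stated, that age predicts change.

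**Working it through.** The plan gives no sample size, SD, dropout rate or covariate correlation, so it has no figure of its own to reproduce on this point.

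**Algebra.** For child i at visit t, let Y_it = μ_t + δ_t·G_i + β′x_i + e_it, where G is the arm, x holds the three time-constant covariates, and each child's errors have covariance S. Let C hold the three change contrasts, so that C′1 = 0.

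1. C′Y_i = C′μ + C′δ·G_i + (β′x_i)·C′1 + C′e_i. The covariate term is zero.
2. The remaining information is the weighted mean 1′S⁻¹Y_i. Its covariance with the contrasts is C′S·S⁻¹1 = C′1 = 0.
3. The covariates therefore act only through the weighted mean. With complete data, the condition-by-time estimates are the arm differences in mean contrasts, for any S and with or without x. Within-arm time contrasts in completers are unchanged by the same argument.
4. Standard errors and F depend on C′SC. Under a random intercept or an unstructured S, C′SC is estimated from the contrasts alone, so these do not change either. Under AR(1) or visit-specific variances, the same parameters also describe between-child variation, so they can change.

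**Numerical check.** REML fits to simulated complete four-visit data. All inputs are assumed: N = 60, 120 or 200 completers in total, person SD 0.7, residual SD 0.7, covariates related to the outcome, and an age-by-time slope of 0.1 per visit per 7 months of age. The table shows F for condition by time (3 numerator df), without / with main-effect covariates.

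| Covariance | N = 60 | N = 120 | N = 200 |
|---|---|---|---|
| Random intercept | 1.429126 / 1.429126 | 2.608397 / 2.608397 | 4.915058 / 4.915058 |
| Unstructured | 1.505771 / 1.505771 | 2.628437 / 2.628437 | 5.442100 / 5.442100 |
| AR(1) | 1.217 / 1.208 | 3.216 / 3.088 | 5.227 / 5.091 |
| Random intercept + visit-specific residual variances | 1.503 / 1.461 | 2.728 / 2.633 | 5.261 / 4.992 |
| Independent visit-specific variances | 0.463 / 0.711 | 0.964 / 1.307 | 1.685 / 2.382 |

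The interaction estimates agreed to about 1e-14 in every row. With covariate-by-time terms, the random-intercept F became 1.885, 2.662 and 5.357, and the unstructured F became 1.940, 2.603 and 5.781. F need not rise, because the estimate moves too.

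**Where the covariates do act.** With some later visits missing (random intercept), F moves from 2.334 to 2.266, from 2.089 to 2.138, and from 4.274 to 4.123. In the complete data at N = 120, the condition term (the arm difference at pretest) moves from -0.450 (SE 0.231) to -0.206 (SE 0.195).

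**Possible size, on assumed inputs.**

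- Imbalance: with n completers per arm, P(difference of at least 0.2 SD in one covariate) = P(|Z| > 0.2/√(2/n)). This is 0.206 at n = 80 and 0.157 at n = 100. For at least one of three independent covariates it is 1 − 0.794³ = 0.50 and 1 − 0.843³ = 0.40.
- Precision: the variance of a change contrast is multiplied by about 1 − R², where R² is the share of the variance of change that is explained. R² of 4–8% gives a 4–8% reduction. In SE this is 1 − √0.96 = 2.0% to 1 − √0.92 = 4.1%.
- Cost of estimating three slopes: a variance factor of about 1 + 3/(N − 6). This is 1 + 3/154 = 1.019 at N = 160 and 1 + 3/194 = 1.015 at N = 200, or about 1% or less in SE.

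**The case against.** The strongest reply is that the gap is inferred from silence. The plan does not exclude covariate-by-time terms, and the interactions it spells out elsewhere are hypotheses under test rather than nuisance terms. That is fair as far as it goes. Main effects remain the ordinary reading of control variables, and if the sponsor intends more, the same sentence needs to say so.

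Second, the phrase about pre-test may qualify BMIz alone, so age might be taken at each visit. In the simulation, per-visit age with irregular visit timing moved the random-intercept F (2.608 to 2.748 at N = 120). With visits on schedule, age at each visit is pretest age plus a constant for that visit. The time effect absorbs that constant, and the cancellation stands.

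Third, the arms are randomized. Chance imbalance is already reflected in the standard error and leaves the test valid. The 40–50% imbalance figure describes ordinary randomization, not a fault. This stands: covariate-by-time terms are an efficiency choice, and nothing here makes the Type I error rate wrong.

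Fourth, a reader might infer from the moderator list that the plan expects age, sex and BMI to predict change. It does not say that. Moderation asks whether the program effect differs between subgroups. Conventionally specified moderator models would carry a moderator-by-time term, but they run one moderator at a time and do not adjust the main test.

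**Conclusion.** The point holds in this form: if the three covariates are time-constant main effects, they leave the condition-by-time estimates among four-visit completers unchanged. The standard errors and F are also exactly unchanged under a random-intercept or unstructured covariance, but not in general, and the plan names no structure.

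Two stronger readings are not supported. One is that the covariates control nothing: they can affect the condition term, the paired comparisons on all available data, the dosage models and the multinomial BMI regression. The other is that the program effect is biased: random assignment protects against bias at assignment, so the loss is precision and adjustment for chance or completion-related imbalance.

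The size of the loss cannot be computed from the documents. If a covariate explains 4–8% of the variance of change, the forgone reduction in the variance of the contrast is about 4–8%, before the small cost of estimating the slopes. If the covariates do not predict change, it is near zero. This is a worthwhile, inexpensive improvement and not a threat to validity.

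**What to change.** In the Data Analyses section, replace the sentence on control variables with one that enters child sex, age in months at pretest and BMIz at pretest, each mean-centred and each with its interaction with time, in every multilevel model that tests condition by time. Use the same terms in the corresponding simple-effects and paired-time-point models. Centring keeps the within-arm time effects interpretable at the average covariate values. State in the same place that age is fixed at pretest, and name the covariance structure, since that determines whether covariates affect the standard errors.

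The cost is a sentence or two and nine model terms (3 covariates × 3 time contrasts), using data already due to be collected. It uses a few degrees of freedom, and the SE increase is negligible if the covariates do not predict change.

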Families (parent/child dyads) will be recruited from Head Start centers in Houston, Texas and childcare centers serving families with low incomes in Pasco, Washington. The Pasco centers will be similar to Head Start in that they provide free services and support for families with low incomes. The goal of these centers is to ensure that all children enter kindergarten ready to succeed. Children who are 3 to 5 years of age with their parent identifying as Hispanic will be considered eligible. Exclusion criteria include: parent under the age of 18 and parent and/or child had major food allergies, diabetes, or were on special diets, including those who were vegetarian. Upon completion of pretest assessments, the project coordinator at each site will use a computer-based randomization tool to assign participants to 1 of 2 arms using simple randomization. Research staff members will work closely with the child development centers regarding recruitment procedures. Recruitment activities will be conducted during registration of children at the centers, parent meetings and drop off and pick up times. Specifically, research staff will explain the goal and activities of the study to interested parents and parents will complete informed consent procedures should they choose to participate in the study. The parent who is primarily involved in feeding the preschool child will be designated as the target parent. The study will be reviewed and approved by the Institutional Review Boards at Baylor College of Medicine and Washington State University. Parents will provide informed consent for themselves and their children before taking part in the study and assent will be obtained from the children as well.

PROGRAM FIDELITY

Observers trained in the curriculum content will conduct fidelity observations on 40% of the lessons. Based upon observer availability, the observations will be distributed across parent, child and family sessions. Facilitators will not be notified in advance that they would be observed. Observers will be different from the facilitators delivering the curriculum. Fidelity will be defined as the number of 'yes' responses reported by the observer (signifying that the facilitator adhered to the lesson component as described in the curriculum) divided by the total number of possible responses (i.e., yes, some, and no).

MEASURES

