Finally, to examine dosage effects, the multilevel analyses will be rerun for those variables showing significant condition by time interactions. In these analyses, only data from parents in the prevention conduction at post-test, 6-months, and 12-months will be examined to determine if the number of sessions parents attended predict their subsequent responses on questionnaire assessments (the pre-test assessments will not be included in these analyses because these sessions occurred *before* parents attend any classes). In conducting these analyses, the condition variable will be replaced by a variable assessing the number of lessons attended (values ranging from 0 to 7). To determine if the dosage effects vary by time point, a separate set of analyses will include the “lessons attended by time” interaction as a predictor (along with the corresponding main effects).

A multinomial logistic regression will be used to examine the effects of the program on children's BMI category (i.e., healthy weight, overweight, and obese). This regression will examine the main effect of condition, controlling for the same variables as in the multilevel

analyses (i.e., child sex, child age in months, and child BMI *z*-score at pretest).

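### Site is left out of the main multilevel models and the BMI-category regression, so site differences in change stay in the error term and chance site imbalance goes unadjusted in the BMI-category result

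*Combined protocol and SAP*

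**What the plan says.** The Study Design section describes a two-site trial ("A randomized controlled trial will be implemented across 2 sites"), with one urban site in Texas and one agricultural community in Washington. Under Participant Eligibility and Recruitment, the Houston families come from Head Start centers and the Pasco families from comparable free childcare centers. Allocation is local and unrestricted: "the project coordinator at each site will use a computer-based randomization tool to assign participants to 1 of 2 arms using simple randomization". No blocking or stratification is mentioned.

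The Data Analyses section sets the covariates: "Child sex, child age in months, and child BMIz at pre-test will be control variables in all of the multilevel analyses". The multinomial model for child weight category tests the main effect of condition, "controlling for the same variables as in the multilevel" analyses, so site is absent there too.

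Site appears once, in reruns of the multilevel models with one moderator at a time: "child age, child sex, child BMI status, and location (Houston versus Pasco"). For these, "Moderation will be tested by examining the significance of the moderator by condition by time interactions". The main models are restricted to families observed at all four assessments; the follow-up comparisons of two time points use whatever data are available.

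**The concern.** The two sites differ in setting and in the type of center, so they may plausibly differ in how feeding measures, eating behavior and child weight develop over a year. Simple randomisation does not force the arms to have the same site mix. A design variable that is known at allocation and may be prognostic would normally be in the main model. Here it is used only in a separate question about effect modification, which does not adjust the main result.

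Two things are at stake. In the multilevel models, any difference between sites in change over time is left as unexplained variation in the condition-by-time test, a test that the plan itself describes as having limited power. In the BMI-category regression, the quantity tested is a condition main effect, so a chance difference in site mix can move it unless the pretest BMI z-score already carries the site difference.

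**Working it through.** **Inputs from the documents:** two sites; simple randomisation at each; covariates sex, age and pretest BMI z-score; four time points; three child weight categories. The documents give no sample size, site split, site difference or within-family correlation on this point, so there is no stated figure to reproduce.

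**Assumptions:** sites of equal size, 120 to 240 families in total, site differences d of 0.2 to 0.8 SD, within-family correlation 0.5, two-sided alpha 0.05.

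**Step 1. Site difference constant over time.** If a site adds the same amount at every visit, that amount drops out of each family's change from pretest. As a check, random-intercept models were fitted to one simulated set of 160 families with four visits and a constant site difference of 0.8 residual SD. The three condition-by-time estimates were -0.1951, 0.2267 and 0.2460, each with standard error 0.2232. They were identical with and without a site main effect. Adding site-by-time terms when the sites did not differ in trend gave a standard error of 0.2235, so the price of the extra terms is negligible.

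**Step 2. Site difference in change.** With correlation 0.5 and unit variance at each visit, the variance of change is 2(1 - 0.5) = 1. An omitted two-level site factor with equal sites adds d²/4.

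| d (SD) | Variance factor 1 + d²/4 | Reduction in SE if site is modelled, 1 - 1/√(1 + d²/4) |
|---|---|---|
| 0.2 | 1.01 | 0.5% |
| 0.5 | 1.0625 | 3.0% |
| 0.8 | 1.16 | 7.2% |

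Simulations of 4,000 trials with 160 families and a 0.5 SD site difference in trend agree: the empirical standard error fell from 0.1639 to 0.1603 (2.2%) and from 0.1657 to 0.1611 (2.8%). With a 0.2 SD difference in trend it moved only from 0.1620 to 0.1619.

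For scale, a 0.4 SD effect with 90 families per arm has power 76.5% with site modelled, and 74.0% with site omitted when d = 0.5.

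**Step 3. Chance imbalance in site mix.** The SD of the between-arm difference in site share is 2√(0.25/N): 9.1, 7.5 and 6.5 percentage points at N = 120, 180 and 240. Equivalently, with n per arm it is √(0.5/n). The chance of a difference of at least 10 points is then 0.32, 0.22 and 0.16 at n = 50, 75 and 100.

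**Step 4. Consequence for a condition main effect.** On a linear scale the shift is imbalance × d. With d = 0.5 its SD is 0.046, 0.037 and 0.032 outcome SDs at N = 120, 180 and 240. A 10-point imbalance gives 0.10 × 0.5 = 0.05 SD. The standard error √(2/n) is 0.20 at n = 50 and 0.14 at n = 100, so this shift is about 0.25 to 0.35 of a standard error. For the BMI-category model these figures are only a guide: d must be read as the site difference left after adjustment for pretest BMI z-score, and the model is logistic rather than linear.

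**The case against.** The strongest reply is that nothing here is an error. Unrestricted randomisation at two sites behaves like a single unrestricted list, so omitting a prognostic covariate is a permitted choice. This stands, given the same allocation ratio at both sites. The plan's description of wave sizes ("Approximately 8 to 10 families will participate in each of the prevention and control conditions at each wave") fits equal allocation. A reader might infer that the main results are biased or their standard errors wrong because site is missing; the documents do not support that.

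A reader might also infer that chance site imbalance contaminates every condition-by-time result. Step 1 shows that it does not for constant differences in complete four-visit data. The follow-up paired comparisons use all available data, so exact cancellation is not assured there.

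A third tempting reading is that wave should be adjusted for as well. The documents do not say that allocation was restricted by wave, or that wave is an analysis variable. A wave main effect would leave the within-family contrast unchanged, for the reason in Step 1. Wave-by-time terms would be costly: at 16 to 20 families per wave and an assumed 100 to 200 families there are about 5 to 12 waves. Beyond site, that means (5 - 2) × 3 = 9 to (12 - 2) × 3 = 30 extra terms.

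Three further points limit the size of the concern:

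- Lost precision and chance imbalance are largely one harm seen from two sides, and should not be added together.
- Pretest BMI z-score probably absorbs much of any site difference in weight category. In a multinomial logistic model, adding a covariate also changes the conditional odds ratio and need not shrink its standard error.
- The plan does check nesting: "Because participants will be nested within classes, the intraclass correlations (ICC's) will be first examined for each dependent variable". A retained class term might take up some site variation. This is partial cover only, because it depends on the check and the plan does not say how control families, who receive no curriculum, map to classes.

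The location rerun does contain site, but as a secondary analysis of a different question.

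**Conclusion.** The omission of site is confirmed in both model types, and it is a matter of efficiency and conditional balance, not validity. For the condition-by-time test, only site differences in change matter. Modelling them would lower the standard error by about 2-3% if the sites differ in trend by 0.5 SD, and by very little if they differ by 0.2 SD. For the BMI-category main effect, chance site imbalance is unadjusted beyond what the pretest BMI z-score absorbs; the linear guide puts a 10-point imbalance at 0.05 SD when the remaining site difference is 0.5 SD. These sizes rest on assumed sample sizes, equal sites and assumed site differences, none of which the documents fix. The change is worth making because it is nearly free and settles an analyst's choice in advance, not because a large gain is expected.

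**What to change.** In the Data Analyses section, add site (Houston or Pasco) and site-by-time as prespecified fixed terms in all multilevel condition-by-time models, including the comparisons of pairs of time points. The site-by-time term is the one that does the work; a site main effect alone would not change the within-family contrast. Add site to the multinomial BMI-category regression. Keep the location moderator run as a separate analysis, and do not add a wave main effect.

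The cost is a change of wording and a few parameters: with four time points, one site term plus three site-by-time terms per multilevel model (one plus one for a paired comparison); with three weight categories, one site coefficient for each of the two non-reference categories. No new data are needed, since the plan already uses location as an analysis variable.

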To control for Type I error, the critical *p* values for each assessment will be determined with the unweighted Bonferroni method,⁵⁸ dividing the critical value of *p* < .05 by the number of comparisons conducted for a given assessment. As discussed in Shaffer,⁵⁸ corrections for familywise error involve correcting alphas separately for each family of hypotheses. Although defining families is a rather straightforward process in a simple experiment (e.g., 1 family in a study with a single dependent variable and 1 independent variable with several levels), Shaffer argues that defining families becomes more complicated (and potentially more problematic) in large, more complex studies where alpha corrections can substantially lower statistical power (i.e., increase Type II error). To balance concerns about Type I and Type II error, a family will therefore be defined as the set of measures derived from a particular outcome assessment, and an alpha correction procedure will then be used (the unweighted Bonferroni) to control for error-rates within families. The resulting critical *p* values will be: FPI, 0.05/16 = 0.003; CFSQ, 0.05/3 = 0.017; FKQ, 0.05/6 = 0.008; compensation trials, 0.05/1 = 0.05; EAH, 0.05/1 = 0.05; FPQ, 0.05/2 = 0.025; CEBQ, 0.05/8 = 0.006; BMI, 0.05/2 = 0.025. Only results that meet these critical values will be reported in the primary analyses. To minimize the probability of Type II error, these critical values will be applied only to *p* values for the simple main effects analyses of time given the limited power of condition by time interactions in this type of design.⁵⁹

Finally, exploratory analyses will be run on variables that show condition by time interactions in the pre-post analyses reported by [name] and colleagues⁴⁵ but do not show significant interactions in the current study. Because the smaller samples at follow-up may reduce the power to find significant time by condition interactions at 6- and 12-months, simple main effects analyses of time were be run separately for the control and prevention groups to determine if the condition effects found in earlier pre-post analyses¹⁶ persisted for the variables in the current study.

REFERENCES

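### The multilevel models do not adjust for the outcome's own pretest, so the between-arm tests are unbiased but less precise than the same data allow

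*Combined protocol and SAP*

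**What the plan says.** STUDY DESIGN sets four assessments in both arms: "prior to the prevention program (pretest), after the program (posttest), and at 6- and 12-month follow-ups". PARTICIPANT ELIGIBILITY AND RECRUITMENT places allocation after the first of them: "Upon completion of pretest assessments, the project coordinator at each site will use a computer-based randomization tool" to assign families by simple randomisation.

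DATA ANALYSES puts every outcome except child weight status into multilevel models. The covariates are fixed: "Child sex, child age in months, and child BMIz at pre-test will be control variables in all of the multilevel analyses". The effect of the program is read from the condition by time interaction: "Significant condition by time interactions will be followed up with simple main effects analyses and multi-level analyses comparing pairs of time points". The analysis set is limited: "The main analyses will be conducted on participants who have data at all 4 time points".

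The dosage analyses are the only place where pretest is taken out of a multilevel model: "the pre-test assessments will not be included in these analyses because these sessions occurred" before any class was attended. The multinomial regression for BMI category is separate and already adjusts for pretest BMI z-score.

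The section later says that the Bonferroni limits go only to *p* "values for the simple main effects analyses of time given the limited power of condition by time interactions in this type of design".

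**The concern.** The outcome's own pretest appears in the main models only as the first of four response occasions. Pretest BMIz does not stand in for the pretest score on a feeding questionnaire, the compensation trial or the eating-in-the-absence-of-hunger task. No constraint that the arms share a pretest mean is described. The fixed effects and covariance structure are not written out, so a free pretest mean in each arm is an inference. It is, however, the usual meaning of a condition by time test with no such constraint, and the explicit removal of pretest from the dosage models supports it.

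Because pretest comes before allocation, the two arms have the same expected pretest mean among all randomised families. A model that estimates two separate pretest means ignores this knowledge. At stake is precision: wider confidence intervals and lower power for the between-arm comparison, in a plan that itself regards that comparison as short of power.

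**Working it through.** **Inputs.** From the documents: two arms, four occasions, pretest before allocation, covariates without the outcome's own pretest. Not in the documents, hence assumed: correlation rho between occasions of 0.3, 0.5 and 0.7 (0.9 as a high case); equal allocation; equal variances (SD = 1); complete data; no class effect; two-sided 0.05; and, for power only, n = 75 per arm with d = 0.4 SD. The plan has no sample-size or power figure to reproduce.

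**One follow-up.** Variances are in units of 2/n.

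- Free pretest means (difference in change): 2(1 − rho).
- Adjusted for pretest: 1 − rho².
- Ratio, adjusted to free: (1 − rho²) / [2(1 − rho)] = (1 + rho)/2.

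| rho | Free | Adjusted | Variance ratio | SE ratio | Fall in SE | Extra families that would give the same gain |
|---|---|---|---|---|---|---|
| 0.3 | 1.40 | 0.91 | 0.65 | 0.806 | 19% | 1/0.65 − 1 = 54% |
| 0.5 | 1.00 | 0.75 | 0.75 | 0.866 | 13% | 1/0.75 − 1 = 33% |
| 0.7 | 0.60 | 0.51 | 0.85 | 0.922 | 8% | 1/0.85 − 1 = 18% |
| 0.9 | 0.20 | 0.19 | 0.95 | 0.975 | about 3% | 1/0.95 − 1 = 5% |

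A simulation with 80 per arm, 5,000 runs and a true effect of 0.30 gave variance ratios of 0.655, 0.757 and 0.844 at rho 0.3, 0.5 and 0.7, and both estimators averaged about 0.30. The difference is in precision, not bias. Below rho 0.5 the change contrast is also less precise than ignoring the pretest, since 2(1 − rho) > 1.

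**Joint 3-df test, compound symmetry.** Let e1, e2, e3 be the effects at the three follow-ups, S1 their sum and S2 the sum of their squares. The noncentrality is:

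- free pretest means: (n/2)(S2 − S1²/4)/(1 − rho);
- common pretest mean: (n/2)[S2 − rho·S1²/(1 + 3rho)]/(1 − rho).

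Constant effect (d, d, d): the bracketed terms are 0.75d² and 3d²/(1 + 3rho), so the gain factor is 4/(1 + 3rho).

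Posttest only (d, 0, 0): the terms are 0.75d² and d²(1 + 2rho)/(1 + 3rho), so the factor is (4/3)(1 + 2rho)/(1 + 3rho).

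Halved at 6 months and gone at 12 (d, d/2, 0): S2 = 1.25d² and S1² = 2.25d², so the terms are 0.6875d² and d²[1.25 − 2.25rho/(1 + 3rho)].

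| Effect pattern | rho 0.3 | rho 0.5 | rho 0.7 |
|---|---|---|---|
| Constant | 2.11 | 1.60 | 1.29 |
| Fading (d, d/2, 0) | 1.30 | 1.16 | 1.08 |
| Posttest only | 1.12 | 1.07 | 1.03 |

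**Power, n = 75 per arm, d = 0.4, rho = 0.5.** Here (n/2)d²/(1 − rho) = 37.5 × 0.16/0.5 = 12. Power is from the noncentral chi-square with 3 df.

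| Effect pattern | Noncentrality, free | Noncentrality, common | Power, free | Power, common |
|---|---|---|---|---|
| Constant | 12 × 0.75 = 9.0 | 12 × 1.2 = 14.4 | 71% | 91% |
| Fading | 12 × 0.6875 = 8.25 | 12 × 0.8 = 9.6 | 67% | 74% |
| Posttest only | 12 × 0.75 = 9.0 | 12 × 0.8 = 9.6 | 71% | 74% |

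**The case against.** The strongest reply is that nothing here is invalid. The interaction contrast is unbiased under randomisation, no error rate is inflated by this choice, and the gain has no known size because rho, the total sample size and the effect size are not stated. That stands. Three further points also stand.

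- The large gains on the joint test belong to a constant effect, which is the most favourable pattern under compound symmetry. The plan treats persistence at follow-up as an open question, so small gains are just as plausible. Class-level variance that arises after allocation is not removed by pretest adjustment and may reduce the gain further.
- A common pretest mean is justified for all randomised families. It is not guaranteed among those with data at all four time points, the set named for the main analyses, because dropout may differ by arm. The change of model should therefore not be made on that set alone.
- Entering pretest as a covariate matches the common-mean model only if its coefficient may differ by time, and only with complete data.

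A reader might infer that the plan relaxes its error control because of power lost through this handling of the pretest. The documents do not support that. DATA ANALYSES attributes the limited power to interaction tests in this type of design, with a citation, and separately mentions smaller samples at follow-up; it never links either to the pretest. The improved model still tests condition effects over time, so the question of which tests receive the Bonferroni values would remain.

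What does not stand is that the gain is therefore negligible: at one follow-up the variance ratio is below 1 for every rho below 1.

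**Conclusion.** The point holds as a matter of efficiency. On the ordinary reading of the models, each between-arm contrast is a difference in change scores and gives up precision that pretest adjustment would recover from data already planned. The loss at one follow-up is moderate at low to middling correlations and slight near 0.9. For the joint test it ranges from substantial to very small according to how the effect behaves over time.

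These sizes rest on assumed correlations, complete data, equal variances and no class effect; the joint-test figures also need compound symmetry, and the power figures need the assumed 75 per arm and 0.4 SD. It would go too far to read the finding as bias, as a promised 20-point rise in power, or as an explanation of the plan's multiplicity rule. BMI category is outside the point. The change is worth making because it costs little and addresses a shortage of power that the plan itself acknowledges.

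**What to change.** For the outcomes in the multilevel models, specify a constrained-baseline mixed model: all four occasions as responses, a common pretest mean across arms, condition effects at posttest, 6 and 12 months, unstructured covariance over time, and the existing covariates. Keep any class-level term that the intraclass correlations call for. Fit it to all randomised families with any available data, not only those with all four time points.

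Alternatively, model the three follow-ups with the outcome's own pretest and its interaction with time as covariates, noting that this is equivalent only with complete data.

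In either case, test condition jointly over the three follow-ups and report the between-arm difference at each with its 95% CI. State the fixed effects and covariance structure in the plan so that the handling of the pretest need not be inferred.

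The cost is a few lines of plan wording and a small change in syntax, with no new data. Which tests receive the Bonferroni values must be settled separately.
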